Aim 2: Isolate the Neurobiological Basis of the "Loss" Research Domain Criteria (RDoc) and the Change Associated with Treatment. Using a factor analysis of the HDRS, we have previously demonstrated that the "loss" RDoC criteria is significantly correlated to MRGlu in frontal cortical areas. We therefore hypothesize that change in MRGlu (pre to post treatment) in these regions will be correlated with symptom improvement specifically in "loss" symptoms. As an exploratory extension, we will determine whether these changes are treatment-specific (i.e. to SSRI or placebo). A validation of our hypothesis suggests a targeted mechanism of action, and provides

a significant step forward for precision treatment. If regional changes in MRGlu are not correlated to improvement in this RDoC category, it suggests that SSRI (or placebo) induced changes may be a downstream effect that should be examined further.

Aim 3: Validate NonInvasive Full Quantification of MRGlu Using Simultaneous Estimation. Full quantification of brain MRGlu with FDG (as performed in this study) requires measuring FDG in arterial plasma (input function) from arterial catheter insertion and blood analysis. This costly and invasive procedure creates a barrier to widespread PET use. Our group has developed an innovative method for Simultaneous Estimation (SimE) of input information and PET outcome measures (e.g., MRGlu). SimE fully quantifies brain MRGlu without requiring an arterial catheter. In the case of FDG, our data suggests that SimE used with a single venous sample can provide accurate results. We further hypothesize that the venous sample may be entirely replaced by study data (e.g., injected dose) and biometrics (e.g., body surface area, lean body mass index). Using two different approaches (statistical imputation and physiological parametric modeling) and previously collected data, we will train the SimE for accurate quantification in the absence of blood data. The rich data collected in this study will then provide a robust benchmark for validation of the SimE approach.

B. BACKGROUND AND SIGNIFICANCE:

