Aim 2: The change in MRgIu from pre to post treatment (SSRI and placebo) will be calculated in the midbrain cluster defined by our preliminary studies. The correlation between this value and Δ HDRS will be assessed with both SSRI and placebo groups as well as with separate cohorts, to determine if there is an effect of treatment. As with Aim 1, a post hoc analysis will also be performed examining this correlation over all voxels.

Power Analysis. The partial correlation for each cluster and the factor related to "loss" varies between 0.5 and 0.6, meaning the true correlation ranges between 0.71 and 0.77. Based on this, using a single cohort (n=50), a true correlation as low as 0.39 can be detected with 80% power (two-tailed analysis, Δ =0.05).

When cohorts are combined (n=100 completers, of 120 enrollees), a correlation as low as 0.27 can be detected.

Aim 3: In a previous cohort, we investigated SimE performance with FDG (and four other tracers). The optimal timing for the blood sample used to anchor the FDG SimE estimation was found to be 40 minutes after injection. At this time, FDG venous and arterial samples are essentially interchangeable. Results using this 40-minute blood-based anchor show that SimE-derived MRGlu are close to MRGlu derived using arterial sampling-based estimation: slope 0.730, correlation 0.955 with compartmental analysis slope 0.876, correlation 0.974 with Patlak analysis. Validation: Validation will be considered complete when MRGlu using conventional (Patlak) analysis and arterial samples matches MRGlu calculated with SimE and one venous sample in the proposed study data. The threshold will be a correlation of at least 0.95 and slope of 0.85 in at least 30 subjects.

F. FUNDING STATUS

This study will be funded through the National Institute of Mental Health (R01MH104512-01A1; 1123782-1-70976), the DANA Foundation (Coeus Proposal #20458, PN15125265; 1128493-1-73073), the Brain and Behavior Research Foundation, (Grant #24459; 1134680-1-75849), internal funding from the Department of Computer Science and pilot funding provided by the Department of Radiology for PET/MRI scan costs.

G. DATA and SAFETY MONITORING PLAN (for more than minimal risk studies)

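### Aim 2 claims a link specific to loss symptoms, but no comparison symptom domain is planned, so a correlation with loss change could not show specificity

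*Combined protocol and SAP*

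**What the plan says.** Section A, Aim 2, starts from earlier work: "Using a factor analysis of the HDRS", the investigators found that a loss score was related to MRGlu in frontal cortical areas. The hypothesis for this trial is that pre-to-post change in MRGlu in those regions "will be correlated with symptom improvement specifically in" loss symptoms. The stated interpretation is: "A validation of our hypothesis suggests a targeted mechanism of action". The only negative outcome described is that regional change does not correlate with loss improvement. The one further specificity check concerns treatment arm, not symptom domain: "As an exploratory extension, we will determine whether these changes are treatment-specific".

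Section E, Aim 2, describes another analysis. Change in MRGlu "will be calculated in the midbrain cluster defined by our preliminary studies". Then: "The correlation between this value and Δ HDRS will be assessed with both SSRI and placebo groups as well as with separate cohorts". The outcome is the total HDRS change, and no loss score is analysed. The secondary step is spatial: "a post hoc analysis will also be performed examining this correlation over all voxels". The loss factor appears in Section E only in the power paragraph, as an earlier partial correlation whose covariates are not stated.

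**The concern.** Specificity is a comparative claim. It says that MRGlu change goes with loss improvement more than with improvement in other symptoms. Aim 2 allows for two outcomes, correlated with loss or not correlated with loss. A third outcome, MRGlu change following improvement across all symptoms, has no place in the plan and would be read as support.

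That third outcome is plausible. The loss score is derived from the HDRS, and its items can be expected to improve along with the rest of the scale, though the documents do not say how closely. Anything related to overall improvement would then also correlate with loss change. The trial could report a symptom-specific metabolic mechanism, and offer it as a step towards precision treatment, when the data show only that metabolism changes as patients get better.

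Section E as written cannot address the question at all, because a correlation with the total score carries no information about one symptom domain.

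**Working it through.** **Inputs from the documents.** Section E, Aim 2: two-sided 5% test, 80% power, detectable correlation 0.39 at n=50 (one cohort) and 0.27 at n=100 (cohorts combined).

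**Inputs assumed.** ρ is the correlation of MRGlu change with general improvement (0.3 to 0.5). λ is the loading of loss change on general improvement (0.6 to 0.8). Neither is in the documents.

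**1. The plan's own figures.** The detectable r is tanh((1.960 + 0.842)/√(n−3)).
- n=50: tanh(2.802/6.856) = 0.387, which agrees with 0.39.
- n=100: tanh(2.802/9.849) = 0.277. Power at 0.27 is 78%, so the stated figure looks truncated, but the difference is small.

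**2. Simple loss correlation when nothing is loss-specific.** If MRGlu change relates only to general improvement, its expected correlation with loss change is ρλ. The chance of significance is Φ(√(n−3)·atanh(ρλ) − 1.960). Example: ρ=0.4 and λ=0.7 give r=0.28 and atanh(0.28)=0.2877. At n=100, 0.2877 × 9.849 − 1.960 = 0.87, or 81%. At n=50, 0.2877 × 6.856 − 1.960 = 0.01, or 50%.

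| ρ | λ | ρλ | n=50 | n=100 |
|---|---|---|---|---|
| 0.3 | 0.6 | 0.18 | 24% | 43% |
| 0.3 | 0.7 | 0.21 | 31% | 56% |
| 0.3 | 0.8 | 0.24 | 39% | 67% |
| 0.4 | 0.6 | 0.24 | 39% | 67% |
| 0.4 | 0.7 | 0.28 | 50% | 81% |
| 0.4 | 0.8 | 0.32 | 62% | 90% |
| 0.5 | 0.6 | 0.30 | 56% | 86% |
| 0.5 | 0.7 | 0.35 | 71% | 95% |
| 0.5 | 0.8 | 0.40 | 83% | 99% |

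**3. Would a partial correlation be enough?** Adjusting loss change for the observed non-loss sum is the obvious remedy. That sum measures general improvement with error, so part of a general effect remains. Take ρ=0.4, loss loading 0.7 and non-loss loading 0.9. The three correlations are 0.28 (MRGlu with loss), 0.36 (MRGlu with non-loss) and 0.63 (loss with non-loss). The partial correlation is (0.28 − 0.36×0.63)/√((1−0.36²)(1−0.63²)) = 0.0532/0.7245 = 0.073. With √(n−4) in place of √(n−3), this is significant in 11% of trials at n=100. For non-loss loadings of 0.8, 0.7 and 0.6 the figures are 24%, 39% and 52%. At ρ=0.57 the range over loadings 0.9 to 0.6 is 20% to 86%.

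**4. Direct comparison of the two correlations.** Williams' test for dependent correlations was simulated with loss and non-loss change loading equally on general improvement (λ 0.6 to 0.9, ρ 0.39 to 0.71, n=50 and 100; 24 scenarios, 10,000 replicates each). A false result, meaning a significant loss correlation that is also significantly larger than the non-loss one, occurred in 2.0% to 2.7% of trials.

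**5. Power of that comparison when the effect is loss-specific.** Take a true loss correlation of 0.39, with the non-loss score related to MRGlu only through loss (its correlation is 0.39 times the loss/non-loss correlation). For loss/non-loss correlations of 0.7 down to 0.3, power is about 36% to 68% at n=100 and 20% to 39% at n=50. The simple correlation has 98% and 81% power at the same 0.39.

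**The case against.** **The criticised test is not in the plan.** Section E never specifies a test of loss change in frontal regions, so step 2 evaluates a plan brought into line with Aim 2. This is correct, and it makes reconciliation the first task. It does not remove the gap: the hypothesis and its interpretation are in Section A, and no section supplies a comparator.

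**The plan may intend partialling.** The power paragraph cites an earlier partial correlation with the loss factor. A reader might infer that the plan rules adjustment out, but the fair statement is that none is specified for the change data. Step 3 shows that adjustment alone would not settle the matter.

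**The protocol is cautious.** A reader might infer that the trial will conclude a targeted mechanism. The text says only that validation suggests one, and it gives no formal decision rule. The inference still does not follow from the test.

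**The rates rest on assumed values.** A reader might infer that a general effect will usually pass as loss-specific. The documents do not support that word. At n=50, four of the nine cells are below 50%, and at n=100 the lowest is 43%. The larger correlations quoted in Section E do not help. The 0.57 concerns pretreatment MRGlu and is called an overestimate there. The 0.71 to 0.77 concerns the loss factor, not general improvement.

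**Conclusion.** The point stands in a limited form. Aim 2 makes a specificity claim that no specified analysis can support, and Section E does not analyse loss at all. Under the stated assumptions, a simple loss correlation would be significant with no loss-specific effect in 43% to 99% of trials at n=100 and 24% to 83% at n=50. The lack of a comparator can be read from the documents, whereas the rates depend on ρ and λ, which cannot. An association between MRGlu change and loss improvement remains a legitimate finding; only the step from association to specificity fails. This should be corrected before analysis.

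**What to change.** 1. Reconcile Sections A and E so that Aim 2 names one set of regions and one outcome.
2. Define loss and non-loss change scores in advance from the HDRS items, with no item in both. Section D already lists the HDRS among the visit assessments, so no new procedure is needed if item scores are kept.
3. Report the correlations of regional MRGlu change with loss change and with non-loss change side by side, and test their difference with Williams' test, two-sided 5%.
4. Williams' test assumes that the two scores are about equally reliable. If they are not, a general effect alone separates the correlations: at ρ=0.4, loadings of 0.8 and 0.6 give 0.32 and 0.24. In that case use a latent-factor model.
5. Give the partial correlation as supporting analysis only.
6. Use *specific* or *targeted* only if the loss correlation is significantly larger than the non-loss one. Otherwise report an association with loss or with general improvement, without a specificity claim.

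The cost is power. For a true loss correlation of 0.39, the direct comparison has the 36% to 68% (n=100) or 20% to 39% (n=50) shown above, and a non-significant difference would not show that specificity is absent. The plan should state this. The simple loss correlation, with its stated power, stays as the test of association. If the investigators judge the power too low, they can drop the specificity wording from Aim 2.

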COMMITTEES ON RESEARCH INVOLVING HUMAN SUBJECTS Established 1971

Protocol Summary Form

TITLE: Advancing Personalized Antidepressant Treatment Using PET/MRI **INVESTIGATORS:** [name] Co-Investigators: [name], PhD, [name], [name], [name], [name], [name], [name] [name], [name], PhD, [name], PhD **Department**: Psychiatry

A. SPECIFIC AIMS:

Despite the burden of failed trials, there are currently no tools for treatment selection in Major Depressive Disorder (MDD). Referring to a recent Positron Emission Tomography (PET) study using 2-[¹⁸F]-fluorodeoxyglucose (FDG), NIMH Director [name] remarked that PET imaging is "on the cusp" of aiding in MDD treatment decisions. To finally realize this goal, the limitations of previous FDG studies must be addressed, including limited sample size, lack of placebo comparison (the placebo effect is a significant obstacle to evaluating treatment mechanism and efficacy), and use of relative outcome measures. In the proposed study, FDG imaging before and after Selective Serotonin Reuptake Inhibitor (SSRI) treatment will be performed using a simultaneous PET/Magnetic Resonance (MR) scanner and: (1) the largest sample size to date; (2) a placebo group; and (3) full quantification using analysis of FDG activity in plasma, which yields more accurate estimates of metabolism than relative activity.

Aim 1: Determine a Pretreatment Marker of SSRI Effectiveness Using PET. With the goal of reducing MDD burden, many studies have assessed the utility of FDG-PET in antidepressant treatment prediction. However, due to the limitations listed above, there is no consensus on which brain regions are predictive of treatment efficacy. In addition to serving as a biomarker of SSRI effectiveness, only conclusive determination of these regions will provide insight into depression pathophysiology, helping uncover SSRI mechanism of action, and aiding in the search of novel therapeutics. Based on our preliminary data and other, similar studies, we hypothesize that SSRI-induced change in the Hamilton Depression Rating Scale (Δ HDRS) will be correlated with pretreatment metabolic rate of glucose (MRGlu, quantified using arterial blood analysis) in three potential regions: (1) midbrain, (2) right anterior insula, and/or (3) left ventral prefrontal cortex.

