Despite current medications, morbidity and mortality of Major Depressive Disorder (MDD) remain high. (Benton, Staab et al. 2007) According to the World Health Organization, MDD affects 121 million people worldwide, and is projected to be the second leading cause of global disability by 2020. Monotherapy with SSRIs is the most widely used treatment for MDD. (Leuchter, Lesser et al. 2008) However, on average, SSRIs require six weeks for onset of action, and two-thirds of those on SSRIs fail to achieve remission.(Trivedi, Rush et al. 2006, Leuchter, Cook et al. 2010) Compounding this problem, patients with residual symptoms are significantly more likely to discontinue treatment or relapse, be hospitalized for medical and psychiatric conditions, or die of suicide and other causes.(Trivedi 2003, Trivedi, Rush et al. 2006, Warden, Trivedi et al. 2007) Although eliminating ineffective treatment trials would significantly reduce patient suffering and healthcare costs, (Taylor, Youngblood et al. 2005, Leuchter, Cook et al. 2010) clinicians currently do not have the tools to objectively select treatment based on an individual's likelihood of remission. Therefore, there is an urgent need to identify markers predictive of an individual's SSRI treatment outcome (Taylor, Youngblood et al. 2005, Leuchter, Cook et al. 2010). Developing this personalized treatment requires increased understanding of the relationship between pretreatment neurobiology, SSRI-induced biological changes, and the corresponding symptom improvements.

Our proposed study, in which FDG-PET scans are acquired before and after escitalopram (or placebo) treatment, avoids these previous limitations by standardizing treatment across all subjects, enrolling 120 subjects to ensure that at least 100 will complete the protocol (largest sample size to date), performing full quantification with arterial blood sampling, and a priori defining the clinical outcome measure as Δ HRDS. Further, we will uncover neurobiological correlates of pathophysiology that span diagnoses.

Potential Noninvasive Estimation: PET research/clinical laboratories have differing levels of software and/or hardware expertise. The key, therefore, to promoting widespread PET use is to develop multiple, validated pathways for noninvasive imaging. In this study, we will evaluate Simultaneous Estimation.

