- 3. Subjects will be recruited through ResearchMatch.org. Potential volunteers will be sent a message through the website providing a brief overview of the study and inclusion criteria. This message will use language that is IRB approved. Volunteers will be able to respond to the message with "Yes, I'm interested" or "No, thanks". If the subject is interested, Research Match will release their contact information to us and they will be contacted by our study team for screening and recruitment.

4. Screening

Patients will first be screened by phone, then in person. All patients will be assessed clinically through history, Structured Clinical Interview for DSM IV (SCID I, though additional questions may be added for consistency with DSM-5), Montgomery–Åsberg Depression Rating Scale (MADRS), review of systems, self-report measures, physical examination, routine blood (~15 ml) for thyroid function and pregnancy tests. Patients may be video or audio-recorded with their consent during the administration of these scales.

INCLUSION CRITERIA	Determined by:
(1) Age range 18 years and above	Interview
(2) Capacity to consent	Interview
(3) Diagnosis of MDD and suffering from a	Interview; SCID-5
major depressive episode	
(4) Score of at least 22 on the MADRS	MADRS
EXCLUSION CRITERIA	Determined by:
(1) Significant active physical illness, particularly those that may affect the brain and use or start of medication during the study that will significantly affect study results	Interview; clinician judgment
(2) Need for use of medication during the study that will interact with the study medication. Need to start medication that will affect study results (anti-epileptics, antidepressants, beta blockers, medications with serotonergic or GABAergic modes of action)	Interview; study clinician
(3) Patients considered at significant risk for suicide	SCID-5; Interview
(4) Patient is unlikely to be able to tolerate medication washout, or the ~3 week interval (5 for fluoxetine) following washout (drug free period). Medication washouts will be supervised by a study physician or nurse.	Interview

(5) For females: Pregnancy, currently lactating;	Interview; HCG urine
planning to conceive during the course of study	
participation, or abortion in the past two	
months.	
(6) Coumadin treatment within 10 days of PET	Medical history
scanning	,
(7) Any MRI contraindications, including metal	Medical History; Interview

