Image Processing: After MRI and PET processing is performed, the data will be processed using the semi-automated analysis pipeline developed in CUBIT. MRI processing includes segmentation (grey, white, csf) and parcellation into different regions of interest. PET processing includes motion correction, coregistration to the MRI, determination of regional activity over time (time activity curves) and modeling of the time activity curves. The modeling requires information about the radioactivity of plasma during the scan. These techniques have been previously described. (Parsey, Ogden et al. 2010, Miller, Hesselgrave et al. 2013) Using this analysis, the metabolic rate of glucose (MRGlu) can be calculated. The arterial input function (as well as Simultaneous Estimation, for comparison) will be used to derive the regional MRGlu.

E. STATISTICS

Aim 1: Correlation between HDRS and pretreatment MRglu will be determined in the ESC and placebo treatment groups in the three specified regions. In post hoc analysis, spatial resolution will be improved through examination of correlation between whole brain voxel MRglu and HDRS using SPM8 on aligned voxel based parametric images. Our group has extensive experience performing these analyses. For both analyses, outcome possibilities include: differential treatment Δ HDRS prediction (i.e. significant correlation, with different sign for placebo and ESC; significant correlation, within different regions, for placebo and ESC; significant correlation in same region, same direction); or insignificant correlation with HDRS for both treatments. The former outcomes would be immediately clinically significant and applicable. The final option, though unlikely based on preliminary data, would also be an important finding and suggest that, either the cohort should be expanded, or additional imaging/clinical measures are needed for prediction.

The power analysis was performed with an estimated 50 subjects per treatment. With a cohort of 50 subjects (on SSRIs), we can detect a true correlation as low as 0.39, with 80% power (two-tailed analysis, Δ = 0.05). In our FDG treatment study, the observed R2 value was 0.32, meaning the true correlation between the data was 0.57 (significantly higher than 0.39). However, this is almost certainly an overestimation because only the voxel cluster highly correlated to the outcome was chosen (as in all cited studies).

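### Aim 1 correlates HDRS change with pretreatment MRGlu without adjusting for baseline HDRS or comparing the arms, so a correlate of severity could be read as a treatment marker

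*Combined protocol and SAP*

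**What the plan says.** Section A, Aim 1 hypothesises that "change in the Hamilton Depression Rating Scale (Δ HDRS) will be correlated with pretreatment metabolic rate of glucose" in midbrain, right anterior insula and/or left ventral prefrontal cortex. Section B counts "a priori defining the clinical outcome measure as Δ HRDS" among the study's advances.

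The region-based analysis is one sentence in Section E: "Correlation between HDRS and pretreatment MRglu will be determined in the ESC and placebo treatment groups in the three specified regions". That sentence omits the Δ, but the rest of the paragraph and Section A show that change is meant. Section E names no covariate for Aim 1. It does not say whether change is absolute or percentage, which rating is the baseline, or which visit supplies the later score. It plans no formal comparison of the arms.

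The same paragraph lists the possible results. A significant correlation in one region with the same sign under escitalopram and placebo is placed with the results contrasted with a null finding, and these are described as clinically usable at once.

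For power, "The power analysis was performed with an estimated 50 subjects per treatment", and with 50 subjects on SSRIs "we can detect a true correlation as low as 0.39, with 80% power (two-tailed analysis, Δ = 0.05" (Δ here evidently stands for alpha).

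On severity, Section A, Aim 2 reports that the "loss' RDoC criteria is significantly correlated to MRGlu in frontal cortical areas". Section C.4 sets the entry threshold: "4) Score of at least 22 on the MADRS". Section D has HDRS rated again after washout.

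**The concern.** A change score contains the baseline score. When patients who start higher tend to change more, anything correlated with the starting score will correlate with the change. If MRGlu in a region reflects how depressed the patient is around the time of the scan, it inherits a correlation with Δ HDRS without carrying any information about drug effect. A simple correlation cannot tell these apart. The same mechanism can hide a real marker whose relation to severity pulls the other way.

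Aim 1 sets out to find a pretreatment marker of SSRI effectiveness. An artefact of severity should appear in both arms with the same sign, and the plan lists that pattern among its successes.

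**Working it through.** **1. The plan's own figure.** With n = 50, 80% power and two-sided 0.05, Fisher's z gives a detectable r = tanh((1.960 + 0.842)/√47) = 0.387. Power at r = 0.39 is 80.6%. The stated 0.39 reproduces.

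**2. Correlation induced by baseline alone.** Suppose MRGlu relates to week-8 HDRS only through baseline HDRS, and Δ is the week-8 score minus baseline. Let ρ = corr(MRGlu, baseline HDRS), k = corr(baseline, week-8 HDRS) and s = SD(week 8)/SD(baseline). Then

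r(MRGlu, Δ) = ρ(ks − 1)/√(1 + s² − 2ks).

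The documents give none of ρ, k or s, so all three are assumed: ρ from 0.2 to 0.6, k from 0.3 to 0.7, s of 1 or 1.4. The rejection rate at n = 50 uses Fisher's z with standard error 1/√47.

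- High end: s = 1, k = 0.3 gives corr(baseline, Δ) = −0.7/1.183 = −0.592. With ρ = 0.6, r = −0.355. Then atanh(0.355) × √47 = 2.54, and the rejection rate is 72%.
- Low end: s = 1.4, k = 0.7 gives −0.02/1.00 = −0.02. With ρ = 0.6, r = −0.012, and the rejection rate is 5%.

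| s | k | corr(baseline, Δ) | ρ = 0.2 | ρ = 0.3 | ρ = 0.5 | ρ = 0.6 |
|---|---|---|---|---|---|---|
| 1 | 0.3 | −0.592 | 13% | 23% | 55% | 72% |
| 1 | 0.5 | −0.500 | 11% | 18% | 42% | 56% |
| 1 | 0.7 | −0.387 | 8% | 13% | 27% | 37% |
| 1.4 | 0.3 | −0.398 | 8% | 13% | 28% | 39% |
| 1.4 | 0.5 | −0.240 | 6% | 8% | 13% | 17% |
| 1.4 | 0.7 | −0.020 | 5% | 5% | 5% | 5% |

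The ρ columns give the chance, per region and arm, of a significant correlation when MRGlu adds nothing to baseline HDRS. With ρ = 0 the rate is 5% throughout.

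**3. Check by simulation.** In 8,000 simulated trials with n = 50, s = 1 and k = 0.3, the simple correlation was significant in 23% (ρ = 0.3) and 56% (ρ = 0.5). Across the scenarios with ρ of 0.3 or 0.5 and k of 0.3 or 0.5, the partial correlation given baseline was significant in 4.8% to 5.2%.

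**4. Role of the entry threshold.** A large-sample simulation assumed rating reliability of 0.7 and a correlation of 0.5 between MRGlu and true severity. When true severity regressed by half, the induced r was −0.24 without selection. With selection on a screening score and a fresh baseline rating it was −0.13 to −0.15. When true severity did not regress, r was 0.00 with or without selection if the baseline rating was fresh, and about +0.1 if baseline error was shared with screening.

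**5. Cost of one covariate.** The detectable partial correlation at n = 50 is tanh(2.802/√46) = 0.391, against 0.387 without it.

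**The case against.** Three stronger readings are tempting, and the documents support none of them.

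- A reader might infer that enrolling at a severity cut-off drives the problem through regression to the mean. Selection is on screening MADRS, HDRS is rated again after washout, and selection mainly shifts the mean change. In most scenarios tested it weakened the induced correlation. The driver is a link between MRGlu and baseline HDRS, together with change that depends on baseline.
- A reader might take Δ HDRS to be a raw difference. The protocol never says so. The arithmetic above assumes it, and the missing definition is a gap of its own.
- A reader might take the 0.5 to 0.6 in the Aim 2 power paragraph as the value of ρ. That is a partial correlation of selected clusters with one HDRS factor, not of an Aim 1 region with total HDRS. The reported link is frontal, so it bears on left ventral prefrontal cortex in general terms and not on midbrain or insula.

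Two further objections carry weight. First, the placebo arm is a real safeguard, since correlations of opposite sign in the two arms are not what a severity artefact predicts. It is incomplete, because no between-arm test is planned and agreement between arms counts as success.

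Second, adjustment is not neutral. Suppose MRGlu correlates 0.6 with stable true severity, reliability is 0.7, and everyone's true change is the same. The change score then correlates 0.00 with MRGlu. Here corr(MRGlu, baseline) = corr(MRGlu, week 8) = 0.6 × √0.7 = 0.502 and k = 0.7. The partial correlation is (0.502 − 0.502 × 0.7)/√((1 − 0.252)(1 − 0.49)) = 0.24, significant in about 39% of trials at n = 50. That result needs zero variation in true change. If variation in true change unrelated to severity raises s to 1.4, corr(MRGlu, week 8) is 0.359 and k is 0.5. The partial correlation falls to 0.14 and the rate to about 16%. This is a reason to show both estimates and compare arms, not to leave baseline out.

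**Conclusion.** The point holds in this form: Aim 1 as written cannot distinguish a region that tracks baseline severity from one that predicts response to the SSRI, and its reading of results does not close that gap. The per-region false-positive rate at n = 50 lies between about 5% and 72%. This assumes an absolute change score, no predictive value of MRGlu beyond baseline HDRS, and the ranges of ρ, k and s in the working. Nothing in the documents says where in that range the trial falls, and at the low end there is no inflation. The case for change rests on a plausible and possibly large bias in the lead aim that is cheap to guard against, not on a demonstrated one.

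**What to change.** In Section E, Aim 1:

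- Define Δ HDRS as the week-8 score minus the HDRS taken after washout and before the first scan.
- Within each arm, regress week-8 HDRS on MRGlu with baseline HDRS as covariate. Using Δ HDRS as the response gives the same MRGlu coefficient.
- Report the unadjusted correlation beside the adjusted estimate.
- Base any claim of an SSRI-specific marker on an MRGlu-by-arm term in a pooled model, with the baseline slope free to differ by arm so that it matches the within-arm fits. Do not base it on correlations of the same sign in both arms.

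This takes a few sentences and no new assessments, since Section D already has HDRS rated after washout and at treatment visits. The covariate uses one degree of freedom. Error in baseline HDRS can leave residual confounding, which is why both estimates are shown.

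The interaction is the weaker test. With 50 per arm and one covariate, the detectable difference in Fisher z is about 2.802 × √(2/46) = 0.584. That corresponds to an adjusted correlation of about tanh(0.584) = 0.53 under escitalopram if it is zero under placebo. A non-significant interaction should therefore be reported with its confidence interval and not read as evidence that the arms agree.
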